7.1.3 End of Treatment

Discontinuation visit

For Part A, a discontinuation visit for safety evaluation should take place as soon as possible after the last administration of avelumab (at least within 7 days) in case treatment was discontinued because of the occurrence of an AE. For Part B, all subjects will have a Discontinuation visit regardless of the reason for discontinuation. The discontinuation visit consists of:

- documentation of AEs and concomitant medication;
- physical examination, including vital signs, and body weight;
- the 12-lead ECGs;
- the laboratory hematology, hemostaseology, and full serum chemistry, and basic urinalysis;
- CCI [REDACTED] CCI [REDACTED];
- ECOG PS; and
- PK sampling (subjects in Part B only).

End-of-Treatment visit

The End-of-Treatment visit is scheduled either 28 days (Part A) or 30 Days (± 5 days, Part B) after the last administration of avelumab, but before any new therapy is started, if possible, whichever occurs earlier. The End-of-Treatment visit will comprise a full assessment for safety, immunogenicity, and tumor response as appropriate, and will include the following (refer to [Appendix I](#)):

- The EQ-5D and FACT-M questionnaires
- AEs, and concomitant medications, ECOG PS
- Physical examination including vital signs, body weight, and skin tumor extent
- The 12-lead ECGs
- The laboratory hematology, hemostaseology, full serum chemistry, and full urinalysis (dipstick plus microscopic evaluation)
- The urine β -HCG pregnancy test (in females of childbearing potential)
- The tumor evaluation per 6 or 12 weekly schedule (only to be performed if no disease progression was documented previously)
- ACTH, ANA, ANCA, RF, T4, and TSH levels
- ADA sampling
- PK sampling (Part B only)
- CCI [REDACTED]
- CCI [REDACTED]
- CCI [REDACTED]

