7.1.4 Safety Follow-up

For Part A, all subjects will have a subsequent visit scheduled 10 weeks after the last administration of avelumab. For Part B, the visit will be 90 days (\pm 1 week). The visit will include the following full assessment of safety parameters (refer to [Appendix I](#)):

- AEs and concomitant medications will be documented, including further anticancer therapy.
- Vital signs and body weight will be measured.
- Physical examination will be performed.
- ECOG PS will be assessed.
- 12-lead ECG will be assessed.
- Laboratory testing consisting of the following will be assessed:
 - Hematology, hemostaseology, core serum chemistry, and basic urinalysis (dipstick only)
 - ACTH, ANA, ANCA, RF, T4, and TSH levels
 - PK sample
 - ADA sample (part B only)
- CCI [REDACTED] CCI [REDACTED]
- A urine β -HCG pregnancy test (in females of childbearing potential) will be conducted.

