7.4.3 Laboratory Assessments

It is essential that the Sponsor be provided with a list of laboratory normal ranges before shipment of study drug. Any change in laboratory normal ranges during the trial will additionally be forwarded to the CRO and the Sponsor.

Blood samples will be taken from nonfasted subjects. All routine laboratory analyses will be performed at a laboratory facility local to the investigational site and relevant results must be available and checked before administration of avelumab.

The report of the results must be retained as a part of the subject's medical record or source documents. Blood samples for the full safety tests listed in Table 7 will be taken from non-fasted subjects during the Screening phase (18 days prior to the first treatment administration), during the treatment phase as specified in the table and in Appendix I, at the End-of-Treatment visit, and at the Safety Follow-up visit. The ACTH, ANA, ANCA, RF, T4, TSH, and urinalysis will only be assessed at the time points defined in Table 7 and Appendix I. If confirmation of a subject's postmenopausal status is necessary, a FSH level will also be performed at Screening, see Section 7.1.1.

Table 7 Required Full Laboratory Safety Tests

Full Chemistry	Hematology
Albumin	Absolute lymphocyte count
Alkaline phosphatase*	ANC
ALT*	Hematocrit
Amylase**	Hemoglobin
AST*	Platelet count
GGT	RBC count
BUN/total urea*	WBC count and differential count
Calcium*	RBC morphology
Chloride*	Reticulocytes
Cholesterol	MCH
Creatine kinase	Mean corpuscular volume
Creatinine*	MCHC
CRP	
Glucose*	Hemostaseology
LDH	aPTT
Lipase**	Prothrombin time/INR
Phosphorus/Phosphates*	
Magnesium*	Basic Urinalysis (dipstick, including macroscopic appearance, bilirubin, blood, color, glucose, ketones, leukocyte esterase, nitrite, pH, protein, specific gravity, urobilinogen) Full urinalysis (dipstick plus microscopic evaluation) to be performed only at the Screening and End-of-Treatment visits and a basic urinalysis prior to each administration of the study drug.
Potassium*	
Sodium*	
Total bilirubin*	
Total protein	
Uric acid	Totality of binding ADAs
Triglycerides	

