Hormone	ACTH, ANA, ANCA, RF, TSH, and T4 For Part A, to be assessed at the Screening visit, Week 13, Week 25, and at the End-of Treatment visit. For Part B, only ACTH, ANA, ANCA, RF, T4, and TSH will be collected at Screening visit, Week 13, Week 25, End-of-Treatment, and Safety Follow-up visits. T4 and TSH to be assessed in Week 1, Week 7, Week 13, and then every 6 weeks while on treatment and at the 30-day End-of-Treatment visit.
FSH (if applicable)	

ADA = antidrug antibody, ACTH=adrenocorticotrophic hormone, ALT=alanine aminotransferase, ANA=antinuclear antibody, ANC=absolute neutrophil count, ANCA=antineutrophil cytoplasmic antibody, aPTT=activated partial thromboplastin time, AST=aspartate aminotransferase, BUN=blood urea nitrogen, CRP=C-reactive protein, FSH=follicle-stimulating hormone, GGT=gamma-glutamyltransferase, INR=international normalized ratio, LDH=lactate dehydrogenase, MCH=mean corpuscular hemoglobin, MCHC=mean corpuscular hemoglobin concentration, RBC=red blood cell, RF=rheumatoid factor; TSH=thyroid-stimulating hormone, T4=free thyroxine, WBC=white blood cell.

* Core serum chemistries in Part A and Part B

** Included in core serum chemistries only for Part B

If a subject has a clinically significant abnormal laboratory test value that is not present at baseline, the test will be repeated weekly and the subject will be followed until the test value has returned to the normal range or the Investigator has determined that the abnormality is chronic or stable.

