8.5.4 Safety Analyses

The on-treatment period is defined as the time from the first study drug administration to the last drug administration date + 30 days or the earliest date of subsequent anticancer drug therapy minus 1 day, whichever occurs first, unless otherwise stated.

Adverse events

All AEs will be coded according to the Medical Dictionary for Regulatory Activities (MedDRA). Severity of AEs will be graded using the NCI-CTCAE v 4.0 toxicity grading scale.

The incidence of TEAEs, regardless of attribution and TEAEs defined as possibly related to avelumab will be summarized by Preferred Term and System Organ Class, and described in terms of intensity and relationship to avelumab. Treatment-emergent AEs (TEAEs) are those events with onset dates occurring during the on-treatment period or if the worsening of an event is during the on-treatment period. Any AEs with an onset or worsening date after the on-treatment period will be reported separately.

Descriptive statistics will be examined for indications of dose-related ADRs.

Laboratory variables

Laboratory results will be classified by grade according to NCI-CTCAE. The worst on-trial grades after the first trial treatment will be summarized. Shifts in toxicity grading from first treatment to highest grade will be displayed. Results for variables that are not part of NCI-CTCAE will be presented as below, within, or above normal limits. Only subjects with postbaseline laboratory values will be included in these analyses.

Physical examination (including vital signs and 12-lead ECGs)

Physical examination including vital signs (body temperature, respiratory rate, heart rate, and blood pressure) and 12-lead ECG as indicated in the Schedule of Assessments ([Appendix I](#)) will be presented.

Further details will be provided in the SAP based on current safety experience applying the latest MedDRA version.

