If a scheduled pre-dose measurement actually occurred post-dose, then the corresponding measurement will be treated and analyzed similar to an unscheduled post-dose measurement.

Baseline for HR and QTc assessments will be derived from the visit where both HR and QT are not missing.

Definition of study day/treatment day:

Treatment day is defined relative to the date of first study drug administration.

Treatment day 1 is defined as date of first study drug administration, the day before is defined as treatment day - 1 (no treatment day 0 is defined).

Definition of on-treatment period:

On-treatment period is defined as the time from the first dose of study treatment through minimum (30 days + last dose of study treatment, start day of new anti-cancer drug therapy – 1 day).

The date of new anti-cancer drug therapy after start date is derived as outlined in [Section 14.2](#).

Standard derivations and reporting conventions:

The following conversion factors will be used to convert days into weeks, months or years:

1 week = 7 days, 1 month = 30.4375 days, 1 year = 365.25 days.

Demographics and physical measurements:

- Age [years]:
 - (date of given informed consent - date of birth + 1) / 365.25
 - In case of missing day, day only: Age [years]: (year/month of given informed consent - year/month of birth)
 - In case only year of birth is given: Age [years]: (year of given informed consent - year of birth)

The integer part of the calculated age will be used for reporting purposes.

- BMI (kg/m²) = weight (kg)/[height (m)]².
- BSA (m²) = ([height (cm) × weight (kg)] / 3600)^{0.5}

For reporting conventions, mean and median should generally be displayed to one more decimal place than the raw data and standard deviation should be displayed to two more decimal places than the raw data. Percentages will be reported to one decimal place. The rounding will be performed to closest integer/first decimal using the common mid-point between the two consecutive values. E.g. 5.1 to 5.4 will be rounded to an integer of 5, and 5.5 to 5.9 will be rounded to an integer of 6.

Unscheduled visits:

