In addition, a listing of all TBILI, ALT, AST and ALP values for subjects with a post-baseline TBILI $\geq 2 \times \text{ULN}$, ALT $\geq 3 \times \text{ULN}$ or AST $\geq 3 \times \text{ULN}$ will be provided.

Parameters with NCI-CTC grades available:

The laboratory toxicities will be tabulated using descriptive statistics (count and percentage) during the on-treatment period. The denominator to calculate percentages for each laboratory parameter is the number of subjects evaluable for CTCAE grading (i.e., those subjects for whom a Grade 0, 1, 2, 3, or 4 can be derived).

- The summary of laboratory parameters by CTCAE grade table will include number and percentage of subjects with Grade 1, 2, 3, 4, 3/4, and any grade (1 to 4) laboratory abnormalities during the on-treatment period.
- The shift table will summarize baseline CTCAE grade versus the worst on-treatment CTCAE grade. The highest CTCAE grade during the on-treatment period is considered as the worst grade for the summary.

The above analyses apply to hematology and chemistry evaluations which can be graded per CTCAE, i.e.:

- Hematology:
Hemoglobin (HB), Leukocytes (white blood cell decreased), Lymphocytes (lymphocyte count increased/decreased), Neutrophils / Absolute Neutrophils Count (ANC) (neutrophil count decreased), Platelet Count (PLT) (platelet count decreased).
- Serum chemistry:
Albumin (hypoalbuminemia), Alkaline Phosphatase (alkaline phosphatase increased), Alanine Aminotransferase (ALT) (ALT increased), Amylase (serum amylase increased), Aspartate Aminotransferase (AST) (AST increased), Total Bilirubin (blood bilitubin increased, Cholesterol (cholesterol high), Creatinine (creatinine increased), Creatine Kinase (CPK increased), Potassium (hypokalemia/hyperkalemia), Sodium (hyponatremia/hypernatremia), Magnesium (hypomagnesemia/hpermagnesemia), Calcium (hypocalcemia/hypercalcemia), Glucose (hypoglycemia/hyperglycemia), Gamma Glutamyl Transferase (GGT) (GGT increased), Lipase (lipase increased), Phosphates (hypophosphatemia), Triglycerides (hypertriglyceridemia).

Parameters with NCI-CTC grades not available:

Hematology and chemistry evaluations which can't be graded per CTCAE criteria will be summarized as:

- Number of subjects with shifts from baseline normal to at least one result above normal during on-treatment period
- Number of subjects with shifts from baseline normal to at least one result below normal during on-treatment period

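### Part B laboratory grade, shift and liver tables stop at last dose + 30 days, so compliant late samples get no graded incidence; one supplementary column would add it

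*SAP*

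**What the plan says.** Part B SAP Section 11 defines the on-treatment period as "time from the first dose of study treatment through minimum (30 days + last dose of study treatment", cut short on the day before new anti-cancer drug therapy if that comes first. Section 17.3.1 applies this limit to four outputs: the CTCAE grade table, the shift from baseline to worst grade, the normal-to-abnormal shifts for parameters without CTCAE grades, and the ALT, AST and bilirubin elevation counts, including concurrent elevations. For the shift table it states: "The highest CTCAE grade during the on-treatment period is considered as the worst grade for the summary".

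The protocol schedules laboratory work beyond that limit. Section 7.1.3 has the End-of-Treatment visit "scheduled either 28 days (Part A) or 30 Days (± 5 days, Part B) after the last administration of avelumab", with hematology and full chemistry. Section 7.1.4 has a "subsequent visit scheduled 10 weeks after the last administration of avelumab. For Part B, the visit will be 90 days", with one week allowed either side, and lists hematology and core chemistry; Appendix I agrees. Section 7.4.3 is broader and has the full tests of Table 7 drawn "at the End-of-Treatment visit, and at the Safety Follow-up visit".

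Protocol 8.5.4 opens with "The on-treatment period is defined as the time from the first study drug administration to the last drug administration date + 30 days". Under laboratory variables it then says: "The worst on-trial grades after the first trial treatment will be summarized". It does not define 'on-trial'.

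**The concern.** The cut-off sits on the nominal day of the Part B End-of-Treatment visit. A value on day 30 counts and a value on day 31 does not, although both visits comply with the protocol. Safety Follow-up lies wholly outside.

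Late values matter for this drug class, and the plan recognises this elsewhere. Protocol 7.1.5 follows subjects for new autoimmune events up to 3 months after the last dose. Protocol 7.4.1.3 runs Part B adverse event reporting to 90 days. SAP Appendix II accepts immune-related onset up to 90 days, although the tables in SAP 17.2.3 are also restricted to treatment-emergent events.

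Take a subject whose ALT of at least 3 x ULN with bilirubin of at least 2 x ULN first appears at Safety Follow-up. That subject enters no liver-elevation category. Liver tests belong to the core panel, so they are drawn at that visit on either reading of the schedule.

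Adverse event reporting fills only part of the gap. Under protocol 7.4.1.1, abnormalities below Grade 3 are generally not reported as adverse events unless they are symptomatic, lead to discontinuation or are judged medically important.

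**Working it through.** The plan gives no figure to reproduce. The check sets the Part B visit windows against the cut-off, counting the last dose as day 0.

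**Inputs**
- On-treatment period ends on day 30 or earlier (SAP Section 11).
- End-of-Treatment: 30 ± 5 days (protocol 7.1.3, Appendix I).
- Safety Follow-up: 90 days ± 1 week (protocol 7.1.4, Appendix I).
- Planned Part B size: 112 subjects.

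**End-of-Treatment.** 30 - 5 = 25 and 30 + 5 = 35, so 11 permitted days. Days 25-30 (6 days) are inside unless a new anti-cancer drug has started. Days 31-35 (5 days) are outside.

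**Safety Follow-up.** 90 - 7 = 83 and 90 + 7 = 97, so 15 permitted days, of which 0 are inside. The visit falls 83 - 30 = 53 to 97 - 30 = 67 days after the cut-off.

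**Discontinuation visit.** It takes place within 7 days of the decision to stop and includes hematology and full chemistry. A decision by day 30 - 7 = 23 puts it inside the window, so an off-drug sample is normally counted.

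**How far a supplementary window must reach**

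| Window ends on day | End-of-Treatment days covered | Safety Follow-up days covered |
|---|---|---|
| 30 (current) | 6 of 11 | 0 of 15 |
| 35 | 11 of 11 | 0 of 15 |
| 90 | 11 of 11 | 8 of 15 |
| 97 | 11 of 11 | 15 of 15 |

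A fixed end at day 90 would cut through the Safety Follow-up window, so the end point should be the visit itself.

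**Effect per subject.** 1/112 = 0.9 percentage points, if all 112 are evaluable for that parameter.

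**What can be graded at Safety Follow-up.** SAP 17.3.1 grades 18 chemistry parameters. In protocol Table 7, five of these are outside the Part B core panel: albumin, GGT, creatine kinase, cholesterol and triglycerides. Calcium is in the core panel but is graded after albumin correction. If only core chemistry is drawn, 5 + 1 = 6 of the 18 cannot be graded at that visit and 12 can, including ALT, AST, bilirubin and alkaline phosphatase.

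**The case against.** The strongest reply is that 30 days is the protocol's own on-treatment definition, applied unless otherwise stated, and that the SAP uses it consistently for adverse events, vital signs, ECG and ECOG status. This stands, and it is why the main tables should stay as they are.

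The second reply is that late data are already reported. All results are listed with dates or visits. A further listing shows every value of any parameter with an abnormal result. Section 11 lets End-of-Treatment and Safety Follow-up values feed the by-visit summaries. The liver listing takes any post-baseline value, and the eDISH peaks carry no stated end. The liver example above would also very likely be recorded as an adverse event and listed as starting after the on-treatment period. All this is true, and a reader who inferred that late values are lost would be wrong. What none of these outputs provides is a count of subjects by grade, shift or liver category. The Safety Follow-up summary also appears only if at least 5 subjects contribute.

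Third, values at days 83-97 may reflect progression, and a single-arm trial has no comparator to separate that from drug effect. This stands as a limit on interpretation and is a reason to keep the late counts supplementary.

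Fourth, the non-core parameters would have shorter follow-up than the rest. This also stands; the fix has to say so.

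**Conclusion.** The point holds for Part B as a low-severity, inexpensive improvement. Compliant End-of-Treatment samples on days 31-35 and all scheduled Safety Follow-up samples get no graded incidence. It changes no efficacy estimate, test or decision rule. The number of subjects whose worst value occurs only after the window is not known from the documents and may be small.

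Three stronger readings are tempting, and the documents do not support them.

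- **Breach of protocol.** Because 8.5.4 says 'on-trial' and SAP Section 9 declares no change, a reader might infer an undeclared narrowing. The term is undefined in a section that opens by defining the on-treatment period, so it may mean exactly that.
- **A share of End-of-Treatment samples excluded.** Five of 11 permitted days is not a proportion of samples. No document gives the distribution of visit days, and 7.1.3 asks for the visit before new therapy where possible, which favours earlier days.
- **Repeat tests reaching only listings.** For a new clinically significant abnormality, protocol 7.4.3 says "the test will be repeated weekly and the subject will be followed until the test value has returned to the normal range". A reader might infer that repeats after day 30 drop out of every summary. SAP 17.3.1 does exclude unscheduled measurements from by-visit statistics, but the visit-window rules in Section 11 include them, so the SAP does not settle it. Where the first abnormal value was on treatment, it is already counted.

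Part A SAP 17.3.1 carries the same limit. The case is made here for Part B.

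**What to change.** Keep the on-treatment tables in Part B SAP 17.3.1. Add one supplementary column to the hematology, core-chemistry and liver-elevation tables. Suggested text:

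> Worst CTCAE grade, shift and liver-elevation category will also be summarized over all samples after first dose through the Safety Follow-up visit and before any new anti-cancer drug therapy. For each parameter, a footnote will give the number of subjects with at least one sample after the on-treatment period.

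Add a note that albumin, albumin-corrected calcium, GGT, creatine kinase, cholesterol and triglycerides may be gradable only through End-of-Treatment, because Safety Follow-up may draw core chemistry only. One further sentence should state how 'on-trial' in protocol 8.5.4 is read for the main tables.

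If no column is added, at least flag laboratory values collected outside the on-treatment period in the listings, as SAP 17.4 already does for vital signs.

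The cost is one extra column per affected table, from data already collected, with the existing tables unchanged. Ending at Safety Follow-up and stopping at new anti-cancer drug therapy are recommendations, not protocol text. The column may add few subjects, and some late values may reflect progression, so it should be labelled supplementary.

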17.3.2 Other Laboratory Parameters

All other parameters collected on the eCRF will be listed in dedicated listings presenting all corresponding collected information on the eCRF.

- Coagulation: activated partial thromboplastin time (aPTT) and prothrombin time (INR).
- Urinalysis: all urinalysis parameters
- Other parameters: hormone, and immunology parameters
- Pregnancy test

The listings of laboratory results will be provided for all laboratory parameters. The listings will be sorted by parameters and assessment dates or visits for each subject. Laboratory values that are outside the normal range will also be flagged in the data listings, along with corresponding normal ranges.

In addition, listings of abnormal values will be provided for hematology, chemistry, urinalysis, coagulation parameters. If there is at least one abnormal assessment for any parameter, all the data for that laboratory parameter will be included into the listing.

For all tests not mentioned above but present in the clinical data, a listing of subjects with at least one result for the relevant test will be provided.

17.4 Vital Signs

Vital sign summaries will include all vital sign assessments from the on-treatment period. All vital sign assessments will be listed, and those collected outside the on-treatment period will be flagged in the listing.

All vital sign parameters will be summarized using descriptive statistics (mean, SD, median, Q1, Q3, minimum, and maximum) of actual values and changes from baseline for each visit over time based on visit windows specified in [Section 11](#). The changes computed will be the differences from baseline.

For each subject the maximum on-treatment increase/decrease from baseline will be calculated and categorized by vital sign measurement (see [Table 7](#)). Missing values will define a separate category.

Table 7 Vital Sign Parameters Change from Baseline Category

| Parameters | Categories of Change from Baseline |
|---|------------------------------------|
| Body temperature increase < 37°C, 37-<38°C, 38-<39°C, 39-<40°C, ≥ 40°C | < 1°C , 1-<2°C , 2-<3°C, ≥ 3 °C |
| Weight increase | <10%, ≥ 10% |
| Weight decrease | <10%, ≥ 10% |
| Heart rate increase <100 bpm ; ≥ 100 bpm | ≤20 bpm, >20 – 40 bpm, >40 bpm |
| Heart rate decrease <100 bpm ; ≥ 100 bpm | ≤20 bpm, >20 – 40 bpm, >40 bpm |
| SBP increase <140 mmHg; ≥ 140 mmHg | ≤20 mmHg, >20 – 40 mmHg, >40 mmHg |
| SBP decrease <140 mmHg; ≥ 140 mmHg, | ≤20 mmHg, >20 – 40 mmHg, >40 mmHg |
| DBP increase <90 mmHg; ≥ 90 mmHg | ≤20 mmHg, >20 – 40 mmHg, >40 mmHg |
| DBP decrease <90 mmHg; ≥ 90 mmHg, | ≤20 mmHg, >20 – 40 mmHg, >40 mmHg |
| Respiration rate increase <20 bpm ; ≥ 20 bpm | ≤5 bpm, >5 – 10 bpm, >10 bpm |
| Respiration rate decrease <20 bpm ; ≥ 20 bpm | ≤5 bpm, >5 – 10 bpm, >10 bpm |

bpm = beats per minute for heart rate and breaths per minute for respiration rate;
DBP=diastolic blood pressure; SBP=systolic blood pressure

The following summaries will be prepared for vital sign parameters as grouped above considering only subjects with post baseline values:

- Maximal Shifts (changes in categories)
- Listing of highest change per subject

An additional subject data listing will present all changes from baseline reported in the highest categories.

